**November 25, 2020**

## STUDY PROTOCOL

1. Background and current status of the issue: the laparoscopic approach for gastric carcinoma (GC) is being increasingly implemented by digestive surgeons. Although recent evidence suggests that this surgical approach is associated with improvements in short-term outcomes, mid- and long-term outcomes have not been well studied.
2. Study justification: laparoscopic gastrectomy for GC is widely employed in eastern Countries. But there is a lack of data on its use and results in Western countries, where the incidence of this pathology is lower.  
but there is much less information on its use in western countries
3. Goals: This study aimed to evaluate the mid- and long-term outcomes of laparoscopic gastrectomy (LG) with D1-D2 lymph node dissection for all stages of GC in a western country.
4. General objectives: to establish a program for the laparoscopic treatment of GC.
5. Specific objectives: determine the short, medium and long-term results of the program.
6. Hypothesis: the results should be similar to those reported by eastern centers.
7. Methodology: prospective observational study.
8. Reference and study population: patients diagnosed of GC and fits for surgery.
9. Inclusion criteria:
  - a. Patients diagnosed with gastric adenocarcinoma and operated by a laparoscopic approach.
  - b. Acceptance the proposed technical procedure by the patient.
  - c. No anesthetic contraindication for the laparoscopic technique.
10. Exclusion criteria:
  - a. Patients lost to follow-up.
  - b. Patients unfit for surgery.
  - c. Palliative surgery.
  - d. T4b lesions or gastric neoplasms other than adenocarcinoma
11. Sample size: 100-150 cases.
12. Variables:
  - a. Demographic data.
  - b. Operative morbidity and mortality.
  - c. Disease-free survival at 3, 5, and 10 years.
  - d. Overall survival at 3, 5 and 10 years.
  - e. Neoadjuvant and / or adjuvant treatment.
13. Data collection and information sources: The data obtained will be collected in an ANONYMOUS database and guarded by the main researcher and the researchers signing the project, respecting at all times Organic Law 15/1999, of December 13, on the Protection of Personal Data.

14. Analysis of data: The statistical program IBM SPSS Statistics 25.0 will be used. A descriptive analysis of the collected data will be carried out, based on survival or mortality during the follow-up period and, later, it will be made with a Cox regression, a univariate and multivariate analysis, with the in order to determine the risk factors for mortality at one year, three, five and ten years of follow-up

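### Overall and disease-free survival at 3, 5 and 10 years are listed as outcomes, but the only descriptive method named, a split by survival or death over an undefined follow-up, estimates none of them

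*Combined protocol and SAP*

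**What the plan says.** The fixed horizons come from item 12 (Variables): "Disease-free survival at 3, 5, and 10 years" under c and "Overall survival at 3, 5 and 10 years" under d. Items 3 and 5 speak only of short-, mid- and long-term results, without naming years.

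Item 14 (Analysis of data) is the whole analysis plan, and it has two steps. The first is descriptive: "A descriptive analysis of the collected data will be carried out, based on survival or mortality during the follow-up period". The second is a model: "it will be made with a Cox regression, a univariate and multivariate analysis", intended to find "risk factors for mortality at one year, three, five and ten years of follow-up".

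The design (item 7) is a "prospective observational study" of 100 to 150 cases (item 11). Patients lost to follow-up are excluded under item 10a. The readable text gives no entry window, minimum follow-up, data-lock date, time origin or censoring rule, and it names no Kaplan-Meier or life-table method.

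**The concern.** The phrase "during the follow-up period" is not tied to any length of time. If patients enter over some years and the data are closed on one date, follow-up is long for the first operated and short for the last. A patient alive six months after surgery and one alive at ten years then both count as survivors. The resulting split depends on when people entered and when the data were closed as well as on prognosis.

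The outcomes in item 12 would then have no valid pre-specified estimator. Item 14 names no analysis of disease-free survival at all, since both of its steps concern death. A table of survivors against deaths would also mix prognosis with length of follow-up, so that a feature commoner among recent patients would look favourable for that reason alone. Item 6 expects results similar to those of eastern centres, and a figure tied to no horizon cannot be set against survival at a stated number of years.

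**Working it through.** The plan has no survival figure to reproduce. Its only design number is 100 to 150 cases, given without derivation, and the point does not depend on it. The check asks what an alive/dead split would show, on average, in a cohort with known survival.

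**Inputs, all assumed.** Uniform entry; constant hazard λ; 5-year overall survival S5 = 0.50, with 0.40 to 0.70 as the range; complete information up to data lock.

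**Truth at S5 = 0.50.** λ = −ln(0.50)/5 = 0.1386 per year. Survival is exp(−3λ) = 0.66 at 3 years, 0.50 at 5 years and 0.50² = 0.25 at 10 years.

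**Expected proportion alive.** With follow-up spread evenly from a to b years, it is [exp(−λa) − exp(−λb)] / [λ(b − a)].

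| Follow-up at lock (years) | Calculation at S5 = 0.50 | Alive | Alive, S5 from 0.40 to 0.70 | Share with potential follow-up of 10 years or more |
|---|---|---|---|---|
| 0–5 | (1 − 0.50)/0.693 | 0.721 | 0.655–0.841 | 0 |
| 0–10 | (1 − 0.25)/1.386 | 0.541 | 0.458–0.715 | 0 |
| 3–8 | (0.660 − 0.330)/0.693 | 0.476 | 0.378–0.679 | 0 |
| 3–13 | (0.660 − 0.165)/1.386 | 0.357 | 0.265–0.577 | 0.3 |
| 10–15 | (0.25 − 0.125)/0.693 | 0.180 | 0.105–0.412 | 1 |

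The same prognosis gives anything from 18% to 72% alive. At 0–5 years the split lies above even 3-year survival (0.72 against 0.66). At 3–8 years it happens to fall near 5-year survival (0.48 against 0.50). At 10–15 years it lies below 10-year survival (0.18 against 0.25).

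**Against sampling error.** The 95% half-width for a proportion of 0.5 is 1.96 × √(0.25/n), which is 0.098 for n = 100 and 0.080 for n = 150. With follow-up of 0–10 years, the gap from 5-year survival is 0.541 − 0.50 = 0.041, inside that margin. The gap from 10-year survival is 0.541 − 0.25 = 0.291, well outside it. With 3–13 years, the gap from 5-year survival is 0.357 − 0.50 = −0.143, outside it in the other direction.

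**Survivors against deaths.** Take follow-up of 0–10 years and divide the cohort by date of entry. The later half (0–5 years) is 0.721 alive. The earlier half (5–10 years) is (0.50 − 0.25)/0.693 = 0.361 alive. Prognosis is identical in the two halves.

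**Comparator.** In 2,000 simulated cohorts with follow-up of 0–10 years and S5 = 0.50, mean Kaplan-Meier estimates were 0.66 at 3 years and 0.50 at 5 years for both n = 100 and n = 150. The standard deviation at 5 years was 0.059 and 0.048 respectively. Ten-year survival cannot be estimated from that follow-up unless the lock falls more than 10 years after the first entries.

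**The case against.** The strongest reply is that the plan does not say the alive/dead split will be presented as 3-, 5- or 10-year survival. That is correct. A reader might infer it from items 12 and 14 together, but the text does not state it. The descriptive wording is loose and could be meant to cover a proper survival analysis. What stands is that no such analysis is named, while a description by survival or death is.

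A second reply is that Cox regression handles censoring and needs the same dates. It does if run on time-to-event data, and the search for prognostic factors is assigned to it and not to the descriptive table, which limits the harm from that table. But its stated purpose is predictors of death, so it does not supply the survival estimates, and it does not cover disease-free survival.

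Third, a reader might infer that the split always flatters long-term survival. The table above does not support this: the error can run either way, and with follow-up of 0–10 years the excess over 5-year survival is only about 3 to 6 points when true 5-year survival is 60% down to 40% (0.626, 0.541 and 0.458 against 0.60, 0.50 and 0.40).

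Fourth, staggered entry is an inference. Item 2 says that incidence in western countries is lower, which says nothing about this centre's caseload, and study dates may stand on pages that are not in the readable text. The inference is still a safe one for a prospective surgical series of this size. If every patient had at least 10 years of follow-up, simple proportions at each horizon would be valid, but nothing in the readable text requires that.

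**Conclusion.** The point holds as a gap between the outcomes listed and the methods named. Followed as written, item 14 produces no valid estimate of overall or disease-free survival at 3, 5 or 10 years, and the description it does name is tied to no horizon when follow-up is unequal. The illustrated size is 18% to 72% alive for one and the same prognosis. That range rests on assumed survival, uniform entry, constant hazard and chosen entry and lock times, none of which the documents give. It shows that the quantity is undefined and does not predict an error of a particular size or direction. No number stated in the plan is shown to be wrong.

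**What to change.** In item 14, replace the description by survival or death with Kaplan-Meier estimates of overall and disease-free survival at 3, 5 and 10 years, measured from the date of surgery, with 95% confidence intervals, numbers at risk and median follow-up. Describe baseline features for the whole cohort and not by final vital status.

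State the entry window and a data-lock date, and censor patients at last contact or at that date. Patients lost to follow-up should be censored in the same way and not removed under item 10a, because a Kaplan-Meier curve computed after removing them would still come from a selected group. Censoring them assumes that loss is unrelated to prognosis, so the number lost should be reported.

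Report the 10-year figure only if follow-up reaches it, and otherwise limit the long-term conclusion to the horizon that follow-up supports.

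The cost is wording in items 10 to 12 and 14. Kaplan-Meier is a standard procedure in the SPSS package already named, and overall survival uses the dates that a time-to-event Cox model needs. Disease-free survival also needs recurrence dates. The downside is that the 10-year result may be delayed or imprecise.

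### Does section 14 of the protocol need to say whether risk factors for death come from one Cox model or from one model per time horizon?

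*Combined protocol and SAP*

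**What the plan says.** Section 14 (Analysis of data) first plans a description of the data by survival or death during follow-up. After that, "it will be made with a Cox regression, a univariate and multivariate analysis" is to be done, "in order to determine the risk factors for mortality at one year, three, five and ten years of follow-up". The regression is named once, in the singular. The section gives no significance level, covariate list, selection rule or multiplicity rule.

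Section 12 (Variables) lists "Overall survival at 3, 5 and 10 years", so one year appears only in section 14. Its other entries that could serve as covariates are demographic data, operative morbidity and "Neoadjuvant and / or adjuvant treatment". Section 11 gives "Sample size: 100-150 cases" without a derivation, and section 7 gives "Methodology: prospective observational study".

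**The concern.** Section 14 ties risk factors to four time points, one of which is not a listed survival outcome. Read literally, that could mean a list of factors for each horizon, each from its own Cox model censored at that horizon. Three things would then be at stake.

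- **False factors.** Each null factor would be tested four times on nested sets of deaths, with no adjustment.
- **One-year imprecision.** Few of 100-150 patients would have died by one year. The hazard ratios would be very uncertain, and modest effects that reached significance would be exaggerated.
- **Misreading over time.** A factor with the same effect throughout could be significant at some horizons and not others, and be reported as an early or late risk factor.

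**Working it through.** The protocol has no figure of its own to reproduce: alpha, power, effect size, event rate and number of factors are all absent. Only the 100-150 patients and the four horizons come from the document. The rest is assumed:

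- two-sided 0.05 per test
- cumulative mortality at 1/3/5/10 years of 5/15/25/40% (low), 10/30/40/50% (mid) or 20/45/55/65% (high)
- a binary factor with 50% prevalence

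**1. False factors if four models are fitted.**

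With independent tests the chance per null factor would be 1 - 0.95^4 = 18.5%. That is only an upper bound, because the horizons share deaths. With independent increments, the correlation between the test statistics at horizons i < j is sqrt(d_i/d_j), where d is the number of deaths. For one and ten years this is sqrt(5/40) = 0.35 (low) and sqrt(20/65) = 0.55 (high).

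Simulating the four correlated statistics gives:

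| Mortality | Null factor flagged at one or more horizons | One model |
|---|---|---|
| low | 14.0% | 5% |
| mid | 12.6% | 5% |
| high | 11.7% | 5% |

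Other mortality and follow-up assumptions gave 9.8-13.6%, hence about 10-14% overall. With 10 independent null factors, the chance of at least one false factor is 1 - 0.95^10 = 40% with one model. With four it is 1 - (1 - 0.117)^10 = 71% to 1 - (1 - 0.140)^10 = 78%.

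**2. One-year precision if a one-year model is fitted.**

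One-year deaths run from 100 x 0.05 = 5 to 150 x 0.20 = 30. The formulas, with d deaths, are:

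- SE(log HR) = 1/sqrt(0.25 d)
- power = Phi(ln HR/SE - 1.96)
- smallest hazard ratio with 80% power = exp((1.96 + 0.8416)/sqrt(0.25 d))

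| One-year deaths | 95% interval at HR 2 | Power at HR 2 |
|---|---|---|
| 5 | 0.35-11.5 | 12% |
| 10 | 0.58-6.9 | 19% |
| 15 | 0.73-5.5 | 27% |
| 30 | 0.98-4.1 | 47% |

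The detectable hazard ratio is 7.25 at 8 deaths, 4.25 at 15 and 2.78 at 30.

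Exaggeration of significant estimates depends on the true effect. At 30 deaths and a true hazard ratio of 3, ln 3/SE = 1.099 x 2.739 = 3.01. Power is Phi(1.05) = 85% and the median significant estimate is 3.2, so there is little inflation. For a true hazard ratio of 2 the median significant estimate is 2.6 at 30 deaths and 5.4 at 8.

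**3. The same quantities if one model is fitted.**

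Deaths by ten years run from 100 x 0.40 = 40 to 150 x 0.65 = 97.5. Each null factor has a 5% chance of being flagged. For a hazard ratio of 2 the interval runs from 1.08-3.72 (40 deaths) to 1.34-2.97 (97.5 deaths), with power 59% to 93%. The problems in steps 1 and 2 do not arise.

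**4. Which reading the text supports.**

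The singular wording and the choice of Cox regression point to one time-to-event analysis. One fitted model gives hazard ratios over the whole of follow-up, and mortality at one, three, five and ten years can be read from the same survival data. The case for four models rests on one loosely written sentence and the added one-year point. That is weak evidence, since one-year mortality needs no further variable.

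**The case for a change.** The strongest case for a change is that nothing in the protocol excludes four models, that risk-factor modelling is the only inferential analysis in section 14, and that a sentence would settle the matter cheaply. The direction of the harm is not in doubt. In simulations with fitted Cox models, a factor with a constant hazard ratio of 2 was significant at some horizons but not all in 26-74% of studies, so a false early or late label would be a real hazard.

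The omission stands, and so does the direction of the harm under four models. What does not stand is the step from there to a required change.

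- **The harm is conditional.** It exists only on a reading that the text does not make and that a singular Cox regression argues against.
- **Some of the size is overstated.** Inflation of significant one-year estimates is not general, as step 2 shows for a true hazard ratio of 3. In the sparsest setting, about 8 one-year deaths, a six-factor model had no finite estimate in about 28% of runs, so the most extreme simulated values are unreliable.
- **The remedy is not free.** Requiring one model would drop horizon-specific results, although section 5 asks for short-, medium- and long-term results. It would also bring proportional-hazards checks that have little power with few deaths.
- **A covariate count cannot usefully be fixed now.** Simulated total deaths ranged from 17 to 125. On a guide of one parameter per 10 deaths, that allows about 1 to 12 parameters, a choice better made when the deaths are known.
- **One model would not remove multiplicity.** With six null factors it still flags at least one with probability 1 - 0.95^6 = 26%. That is usual in exploratory risk-factor work, and a reader should allow for it under either reading.

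**Conclusion.** No change follows. This is missing detail that analysts fill sensibly: followed in the ordinary way, as one Cox model for overall survival on all follow-up, the plan gives sound results. If four unadjusted models were fitted instead, the chance of flagging a given null factor would be about 10-14% rather than 5%, and a one-year model on about 5-30 deaths could not estimate a hazard ratio near 2 with useful precision. Those figures rest on an assumed 0.05 level and assumed mortality. The direction held in every scenario examined; the size is illustrative.

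Risk factors are secondary here. Sections 3 to 6 concern outcomes, the programme and similarity to eastern centres. With an observational design and no stated error rate, no claimed error control is lost. The one-year point in section 14 that section 12 lacks is a minor inconsistency with no effect on the analysis. If a report did present separate factor lists by horizon, the figures above show why differences between the lists should not be read as early or late effects.
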